
## 6 Statistical Considerations

### 6.1.1 Primary Endpoint

The analysis population will include subjects who complete the NRS at both baseline and 6-month follow-up visit. The primary endpoint will be calculated as follows:

Change in pain = pain at 6 months assessed by NRS – pain at baseline assessed by NRS  
Relative Change in pain (%) = (change in pain at 6 months/pain at baseline assessed by NRS)\*100%

Change and relative change (%) in pain will be summarized by mean and standard deviation, median, minimum, maximum and a 95% confidence interval. Results will be descriptively compared to data from existing tonic and BurstDR trials to evaluate efficacy.

### 6.1.2 Secondary Endpoints

The following secondary endpoints will be used to evaluate the relationship between patient characteristics, program usage, and therapy outcomes. Endpoints will be summarized by mean, standard deviation, median, minimum, maximum, and a 95% confidence interval.

#### **6.1.2.1 Change in Quality of life**

The endpoint will be measured using the EQ5D questionnaire. The analysis population will include subjects who complete the EQ5D questionnaire at baseline and at the 6-month follow-up visit. The endpoint will be calculated as a raw difference score as well as relative change reported as a percentage change from baseline.

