### 4.4.1 Inclusion Criteria

1. Subject has chronic, intractable pain of the trunk and/or limbs, including unilateral or bilateral pain associated with the following: failed back surgery syndrome and intractable low back and leg pain.
2. Subject has a score of 6 or higher on the NRS for average pain specific to the area(s) of chronic pain being treated over the past 24 hours at the baseline visit.
3. Subject is considered by the Investigator as a candidate for implantation of a spinal cord stimulator system according to the system Instructions for Use.
4. Subject is 18 years of age or older at the time of enrollment.
5. Subject is willing to cooperate with the study requirements including compliance with the regimen and completion of all study visits.
6. Subject has signed and received a copy of the Ethics Committee/Institutional Review Board (EC/IRB) approved informed consent.

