#### **5.4.1 EuroQol 5- Dimensions Questionnaire (EQ5D) (EuroQol Group, 2009)**

EQ5D is a standardized instrument for use as a measure of health outcome applicable to a wide range of health conditions and treatments. It provides a simple descriptive profile and a single index value for health status. The EQ5D-3L descriptive system comprises the following 5 dimensions: mobility, self-care, usual activities, pain/discomfort and anxiety/depression. Each dimension has 3 levels: no problems, some problems, extreme problems. A visual analog scale (VAS) for health is also included in the measure as a patient-reported estimate of overall health status.

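### The EQ5D percentage change names no score and has no rule for a baseline at or below 0; if the score used is an index that can be negative, the sign reverses for those subjects

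*Combined protocol and SAP*

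**What the plan says.** Section 4.3.2 lists change in quality of life on the EQ5D, from baseline to 6 months, as a secondary endpoint. Section 6.1.2.1 defines its calculation: "The endpoint will be calculated as a raw difference score as well as relative change reported as a percentage change from baseline". Section 6.1.2 sets the summary for all secondary endpoints: "Endpoints will be summarized by mean, standard deviation, median, minimum, maximum, and a 95% confidence interval".

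Section 5.4.1 describes two scores from the same instrument. Of the questionnaire it says: "It provides a simple descriptive profile and a single index value for health status". It adds: "A visual analog scale (VAS) for health is also included in the measure as a patient-reported estimate of overall health status". Neither 4.3.2 nor 6.1.2.1 says which of the two is the endpoint. No value set and no range for the index appear anywhere.

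The only relative-change formula written out is the one for the NRS in section 6.1.1: "Relative Change in pain (%) = (change in pain at 6 months/pain at baseline assessed by NRS", closed by a bracket and multiplied by 100%. The denominator is the baseline with its sign. Section 6.1.4 deals with missing data and with data judged spurious; a valid index value at or below 0 is neither.

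**The concern.** A percentage change keeps its direction only when the baseline is positive. The plan secures that for the NRS, because section 4.4.1 requires: "Subject has a score of 6 or higher on the NRS". It has no such protection for the EQ5D.

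If the EQ5D score can be negative, a subject who starts below 0 and improves is recorded with a negative percentage, and one who starts below 0 and worsens with a positive one. Baselines just above or below 0 give very large values of either sign, and these can dominate the mean. The two planned outputs for one named secondary endpoint, the mean raw difference and the mean percentage change, could then point in opposite directions in the same subjects. The 95% CI does not cure this, because the quantity averaged has the wrong sign in part of the sample.

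**Working it through.** **Inputs from the documents.** Section 6.3 gives 267 enrolled, 10% lost between baseline and trial, 30% trial failure and 14% lost from implant to 6 months: 267 × 0.90 × 0.70 × 0.86 = 144.7, which agrees with the plan's 145. The plan states no figure for the EQ5D endpoint, so there is none to reproduce.

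**Assumed inputs.** The lowest possible index value, and the mean, SD, gain and correlation of the index, are not in the documents. All are assumptions here.

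**Step 1: single subjects.** Percentage change = 100 × (6-month value − baseline) / baseline.

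- −0.10 to 0.60, a gain: 100 × 0.70 / (−0.10) = −700%.
- 0.10 to 0.60, a gain: 100 × 0.50 / 0.10 = +500%.
- −0.20 to −0.40, a loss: 100 × (−0.20) / (−0.20) = +100%.
- 0.02 to 0.52: 100 × 0.50 / 0.02 = +2500%. −0.02 to 0.48: 100 × 0.50 / (−0.02) = −2500%.

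The reversal is certain for any non-zero change from a negative baseline. At a baseline of exactly 0 the percentage is undefined.

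**Step 2: effect on a mean, by hand.** Let every subject gain 0.30, a share q start at −0.10 and the rest at 0.40. The mean is q × (−300%) + (1 − q) × 75%.

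- q = 0: +75%.
- q = 10%: −30 + 67.5 = +37.5%.
- q = 20%: −60 + 60 = 0%.
- q = 30%: −90 + 52.5 = −37.5%.

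The raw mean change is +0.30 in every case.

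**Step 3: simulation.** 145 subjects, 2,000 repeats, true gain 0.25 before clipping, correlation 0.5, equal SD at both visits, normal index clipped at −0.59 and 1. Under this model the share of subjects with a negative baseline is Φ(−mean/SD); for example, Φ(−0.2/0.3) = 25%. The index was left unrounded or rounded to steps of 0.01 or 0.05, and baselines of exactly 0 were dropped. The share column is for the unrounded index.

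| Baseline mean, SD | Subjects with wrong sign | Repeats with negative mean %: unrounded | step 0.01 | step 0.05 |
|---|---|---|---|---|
| 0.2, 0.3 | 25% | 45–47% | 39–41% | about 30% |
| 0.4, 0.3 | 9% | 27–30% | 12–13% | about 1% |
| 0.5, 0.25 | 2% | 12–13% | 3% | 0% |
| 0.6, 0.2 | 0.1% | 2% | under 1% | 0% |

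The ranges are across random seeds. The mean raw change was positive in every repeat. The median percentage change was negative in at most about 4% of repeats in the first row and in none of the others.

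**Step 4: a score that cannot be negative.** With the floor set at 0, the mean percentage change was negative in no repeat in any of the four scenarios.

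**The case against.** The strongest objection is that the decisive premise comes from outside the documents. A reader might infer that the EQ5D index here is known to go below 0. Section 5.4.1 does not say so and names no value set. A reader might also take the index to be the endpoint, but sections 4.3.2 and 6.1.2.1 name only the questionnaire. Both points stand, and they make the sign reversal conditional. They do not remove the gap: the plan commits to a percentage without fixing the score or providing for a baseline at or below 0.

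Nor does an NRS of 6 or higher show that index values will be low. It concerns pain, one of five dimensions, and the documents give no baseline EQ5D figures. This too stands, and it is why the result is shown over a range of baseline means.

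A further objection is that the simulated mean depends on how finely the index is measured. "The EQ5D-3L descriptive system comprises the following 5 dimensions", each with 3 levels, so there are at most 3^5 = 243 health states, and a smooth density near 0 is a modelling choice. This stands. At baseline mean 0.2 the 2.5th to 97.5th centiles of the mean run from about −1500% to +1560% unrounded, but only from about −116% to +150% at steps of 0.01. No single range for the mean can be defended, so none is offered as the size of the problem.

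Finally, the plan also requires the raw difference, median, minimum and maximum. The first two are much less affected, and the last two would expose extreme values. A 95% CI lying wholly below 0 occurred in about 3% of repeats or fewer. This limits the harm, but the mean and its CI are still planned outputs, and the subject-level signs are still wrong.

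**Conclusion.** The point holds in conditional form. Section 6.1.2.1 plans a percentage change for the EQ5D without naming the score and without a rule for a baseline at or below 0. If the index is analysed with a value set that goes below 0, the rule gives a wrong-signed result for every subject with a negative baseline whose score changes, and near-zero baselines dominate the mean.

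The size depends on baseline health. Under the assumptions above, about 25% of subjects are affected and about 30% to 47% of repeats have a negative mean at baseline mean 0.2 (SD 0.3). The figures are about 9% of subjects and 1% to 30% of repeats at 0.4 (SD 0.3), and about 0.1% and under 3% at 0.6 (SD 0.2). If the score cannot be negative, no sign reverses.

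A reader might infer that the plan's quality-of-life result as a whole would be reversed. The documents do not support that: the raw difference is planned in the same sentence and is correct, the median is far more stable, and the 12-, 18- and 24-month EQ5D summaries in section 6.1.3 specify only change. The primary endpoint and sample size are not touched. This is worth correcting because the remedy is simple and nearly free, not because a main conclusion of the study depends on it.

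**What to change.** In section 6.1.2.1:

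- State which EQ5D score is the endpoint (index, VAS or both) and, for the index, the value set.
- For the index, report only the raw change: mean, SD, median, range and 95% CI.
- Limit any percentage change to the VAS, and say what is done if a VAS baseline is 0.

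The cost is a short edit to one paragraph, with no new data and no extra subjects. The small downside is that the index will have no subject-level percentage beside those of the other scales. Using one value set across all countries, or reporting a ratio of group means with a bootstrap CI, is optional and not needed to close this point.

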#### **6.1.2.2 Change in Sleep**

The endpoint will be measured using the MOS Sleep Scale. The analysis population will include subjects who complete the MOS Sleep Scale at baseline and at the 6-month follow-up visit. The endpoint will be calculated as a raw difference score as well as relative change reported as a percentage change from baseline.

#### **6.1.2.3 Change in Physical Function**

The endpoint will be measured using the PROMIS Physical Function Scale. The analysis population will include subjects who complete the PROMIS Physical Function Scale at baseline and at the 6-month follow-up visit. The endpoint will be calculated as a raw difference score as well as relative change reported as a percentage change from baseline.

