#### **5.4.5 Tampa Scale for Kinesiophobia (TSK) (Woby et al, 2005)**

The TSK is a 11-item self-report checklist using a 4-point Likert scale that was developed from the original 17-item checklist (Miller, Kopri & Todd, 1991) as a measure of fear or movement or (re)injury. The scale is based on the model of fear avoidance, fear of work related activities, fear of movement and fear of re-injury (Vlaeyen et al., 1995). The TSK has also been linked to elements of catastrophic thinking (Burwinkle et al., 2005). The scale can be useful in measuring unhelpful thoughts and beliefs about pain in people with chronic pain.

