#### **5.4.7 Patient-Reported Outcome Measure Information System (PROMIS) Physical Function – Short Form Version 1.2**

The PROMIS Physical Function short form is an 8-item instrument designed to measure physical capability rather than actual performance of physical activities. The scale measures universal physical function rather than disease-specific impairment and assesses current function rather than function over a specified time period. Each question has five potential response options ranging in value from one to five to give a total score ranging from 8 to 40. Scores are converted into t-scores where the average for the general US population is 50 and the SD is 10. Higher scores indicate better physical function. This questionnaire is not available in all languages (e.g. Finnish); as such, it is only required at sites where a translation is available.

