#### **5.4.8 Pain Numerical Rating Score (NRS)**

The pain NRS consists of 1 question that will be asked by interviewing the subjects. Patients will be asked to rate, from 0 (no pain) to 10 (worst imaginable pain), their average pain over the past 24 hours specific to the area(s) of chronic pain being treated. A higher score indicates greater pain intensity.

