#### **6.1.2.4 Change in Fear Avoidance**

The endpoint will be measured using the TSK. The analysis population will include subjects who complete TSK at baseline and at the 6-month follow-up visit. The endpoint will be calculated as a raw difference score as well as relative change reported as a percentage change from baseline.

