## 6.3 Overall Sample Size

The study aims to enroll 267 subjects based on assumptions drawn from experience with the Prodigy I study. Assuming a trial failure rate of 30%, and an attrition rate of 10% between baseline and trial, and 14% from permanent implant to 6-month follow-up, 168 subjects are projected to complete the permanent implant and 145 subjects are projected to complete the 6-month follow-up for primary endpoint evaluation. One hundred forty-five (145) subjects with evaluable NRS data at baseline and 6-month visit provides a 95% confidence interval on the NRS change from baseline to 6-month with half interval width of 0.49 assuming the standard deviation of the NRS change is 3.

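### Percentage change from baseline is planned for PROMIS Physical Function, which has no true zero, and for the TSK, which has the same fault if its items are coded 1 to 4

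*Combined protocol and SAP*

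**What the plan says.** Section 6.1.2.3 (physical function) and section 6.1.2.4 (fear avoidance) use the same sentence for the 6-month endpoint: "The endpoint will be calculated as a raw difference score as well as relative change reported as a percentage change from baseline". The opening of section 6.1.2 sets the summary for all secondary endpoints: "Endpoints will be summarized by mean, standard deviation, median, minimum, maximum, and a 95% confidence interval". The percentage would therefore be reported with a mean and an interval, as the difference would.

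The instruments are described in section 5.4:

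- **PROMIS (5.4.7):** "Each question has five potential response options ranging in value from one to five to give a total score ranging from 8 to 40". Then: "Scores are converted into t-scores where the average for the general US population is 50 and the SD is 10". Section 6.1.2.3 names only the scale. It does not say whether the percentage is taken on the raw total or on the T-score.
- **TSK (5.4.5):** "The TSK is a 11-item self-report checklist using a 4-point Likert scale". No numeric coding and no total range are given.
- **NRS (5.4.8), for contrast:** "Patients will be asked to rate, from 0 (no pain) to 10 (worst imaginable pain), their average pain over the past 24 hours". Section 6.1.1 plans a percentage for this scale too.

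For later visits, section 6.1.3 lists only the change from baseline for PROMIS and the TSK and mentions no percentage.

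**The concern.** A ratio to baseline can be read as proportional improvement only if the zero of the scale marks absence of the thing measured. On the NRS it does. On PROMIS it does not: the lowest raw total is 8, and a T-score of 0 is simply five SDs below the US average. If TSK items are coded from 1, the lowest TSK total is 11.

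On such a scale the percentage can be calculated for every subject and looks sound, so nothing in the analysis would flag it. Two of the seven secondary endpoints could carry a mean percentage and a 95% CI whose size reflects in part where the scoring happens to start. A reader used to the NRS percentage may take them to mean the same kind of thing.

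**Working it through.** **The plan's own figures.** No numeric target is stated for PROMIS or the TSK. The only computed design figures are in section 6.3 ("Assuming a trial failure rate of 30%, and an attrition rate of 10% between baseline and trial", then 14% to 6 months). They reproduce: 267 × 0.90 × 0.70 = 168.2; 168.2 × 0.86 = 144.7; 1.96 × 3/√145 = 0.488 (0.492 with the t quantile), against the stated 168, 145 and 0.49. They concern enrolment and the NRS only, and this point does not depend on them.

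**Formula.** With baseline B and follow-up F, the percentage is 100 × (F − B)/B. If the same answers are scored with every total lower by a constant c, the difference F − B is unchanged, but the percentage becomes 100 × (F − B)/(B − c). The difference does not depend on the origin; the percentage does.

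**Inputs.** PROMIS: 8 items scored 1 to 5, total 8 to 40 (section 5.4.7); scoring the items 0 to 4 gives 0 to 32, so c = 8. TSK: 11 items with 4 response options (section 5.4.5). Coding 1 to 4 gives 11 to 44 and coding 0 to 3 gives 0 to 33, so c = 11; both codings are assumptions. All baselines and changes below are illustrative, since the documents give none.

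**PROMIS raw total, gain of 4 points**

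| Baseline (8–40) | Percentage | Same answers, 0–32 | Percentage |
|---|---|---|---|
| 16 | 4/16 = +25.0% | 8 | 4/8 = +50.0% |
| 20 | 4/20 = +20.0% | 12 | 4/12 = +33.3% |
| 24 | 4/24 = +16.7% | 16 | 4/16 = +25.0% |

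**PROMIS T-score.** A gain of 5 points from 35 is 5/35 = +14.3%. In SD units the same subject moves from (35 − 50)/10 = −1.5 to −1.0, and 0.5/(−1.5) = −33.3%. The gain is half an SD in both cases, yet the percentage changes sign.

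**TSK, fall of 6 points.** Coded 1 to 4, 28 to 22: −6/28 = −21.4%. The same answers coded 0 to 3, 17 to 11: −6/17 = −35.3%. With 1 to 4 coding the largest possible fall from 28 is (11 − 28)/28 = −60.7%, so −100% cannot be reached.

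**What is not the fault.** Dependence on baseline alone does not separate these scales from the NRS. A 2-point NRS fall is −2/6 = −33.3% from 6 and −2/10 = −20.0% from 10. The difference is that the NRS origin is fixed by its definition of 0, while the PROMIS origin is a scoring choice.

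**The case against.** The strongest reply is that the percentage is a supplementary column. The absolute difference is planned first, with its own mean, SD, range and 95% CI. Section 6.1.2 gives no test or success threshold for these endpoints, section 6.3 sizes the study on the NRS alone, and section 6.6 has no statistical stopping criteria. All of this stands, and it limits the point to a minor one. It does not make the percentage valid.

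It can also be said that the PROMIS scoring is fixed in section 5.4.7, so no one will rescore it from 0 to 32, and that neither TSK coding is in the documents. Both statements are true. The rescoring is a test of whether the figure has a meaning independent of convention, not a forecast of study conduct. For the TSK the fault is conditional: under 0 to 3 coding it would not arise. But while the coding is unstated, the planned TSK percentage is not uniquely defined.

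Three stronger readings are tempting and are not supported:

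- A reader might infer that the percentage says nothing about the amount of improvement. Under one fixed scoring and at a given baseline it rises with the improvement; it depends on change, baseline and origin together.
- A reader might infer that the plan compares percentages across instruments. No section does so; the descriptive comparison in section 6.1.1 sets pain results against existing trials.
- A reader might infer that the other five secondary scales are clear of the fault. The same sentence appears for each of them, and nothing here shows that they are.

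**Conclusion.** The point holds as a minor one. For PROMIS it rests on the documents alone: neither the raw total nor the T-score has a true zero, so the planned percentage is not proportional improvement whichever metric is used, and section 6.1.2.3 does not say which. For the TSK it rests on the assumption that items are coded 1 to 4.

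In the illustrations, a shift of origin alone moves the percentage by a factor of 1.5 to 2 for the PROMIS raw total (33.3/20.0 = 1.7 at baseline 20) and by 35.3/21.4 = 1.6 for the TSK. The size in this study cannot be given, because the documents contain no baseline values for either scale. It would be wrong to infer that the PROMIS or TSK results as a whole are unsound: the absolute difference is unaffected by a shift of origin.

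**What to change.** In sections 6.1.2.3 and 6.1.2.4 delete the percentage change and keep the absolute difference with its 95% CI. State whether the PROMIS difference is on the raw total or the T-score, and state the TSK item coding.

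Check the other five endpoints that use the same sentence (sections 6.1.2.1, 6.1.2.2 and 6.1.2.5 to 6.1.2.7). The MOS Sleep Scale is the first candidate, since section 5.4.6 codes ten of its items 1 to 6.

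If a unit-free figure is wanted, use one standardiser throughout: the mean absolute change divided by this study's own baseline SD for that scale. Do not mix it with the SD of 10 in section 5.4.7, which belongs to the general US population and not to this sample.

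The cost is a few sentences of wording. No data collection, test or sample size changes, and the 6-month summaries would match the later visits in section 6.1.3, which list only change. The one loss is that these two scales would no longer show a percentage beside that of the NRS. If the change is made without an amendment, section 6.7 already requires it to be documented in the report.

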#### **6.1.2.4 Change in Fear Avoidance**

The endpoint will be measured using the TSK. The analysis population will include subjects who complete TSK at baseline and at the 6-month follow-up visit. The endpoint will be calculated as a raw difference score as well as relative change reported as a percentage change from baseline.

#### **6.1.2.5 Change in Anxiety**

The endpoint will be measured using the STAI. The analysis population will include subjects who complete the STAI at baseline and at the 6-month follow-up visit. The endpoint will be calculated as a raw difference score as well as relative change reported as a percentage change from baseline.

#### **6.1.2.6 Change in Depression**

The endpoint will be measured using the PHQ9. The analysis population will include subjects who complete the PHQ9 at baseline and at the 6-month follow-up visit. The endpoint will be calculated as a raw difference score as well as relative change reported as a percentage change from baseline.

